8.4 Treatment of Overdose

For this study, any dose of bintrafusp alfa greater than 2 times of the planned dose within a 24-hour time period will be considered an overdose. This is based on dose escalation study data in which participants safely received up to 30 mg/kg bintrafusp alfa every 2 weeks (including with doses $>$ 2400 mg) with no observed dose limiting toxicity at 30 mg/kg and not reaching maximum tolerated dose (refer to the IB). Safety at significantly higher doses has not been clinically evaluated.

- In case of overdose with clinical correlation, symptomatic treatment must be used; there are no known antidotes for the compound.
- In the event of an overdose, the study intervention infusion should be discontinued, and participants should be observed closely for any signs of toxicity. Supportive treatment should be provided if clinically indicated.

- Even if not associated with an AE or a SAE, any overdose is recorded in the eCRF and reported to global patient safety in an expedited manner. Overdoses are reported on a SAE and Overdose Report Form, following the procedure in [Appendix 4](#).

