6.1 Study Intervention(s) Administration

Bintrafusp alfa will be administered as a monotherapy in this rollover study (see [Table 4](#)).

Table 4 Study Intervention

Intervention Name	Bintrafusp alfa
Type	Drug
Dose Formulation^a	Sterile concentrate solution for infusion
Unit Dose Strength(s)	10 mg/mL in single-use glass vials (600 mg provided per vial)
Dose Amount	
 • 1200 mg • 2400 mg • Other dose amount as specified in the participant's parent protocol
Frequency	
 • 1200 mg: once every 2 weeks • 2400 mg: once every 2 weeks • 2400 mg: once every 3 weeks • Other dose amount as specified in the participant's parent protocol: once every 2 weeks
Route of Administration	Intravenous infusion
Dosing Instructions	
 • Flat dose of 1200 mg administered over 1 hour (-10/+20 minutes, i.e., over 50 to 80 minutes) once every 2 weeks. • Flat dose of 2400 mg administered over a minimum of 1 hour (-10/+20 minutes) and up to 2 hours (-10/+20 minutes) once every 3 weeks. • Flat dose of 2400 mg administered over a minimum of 1 hour (-10/+20 minutes) and up to 2 hours (-10/+20 minutes) once every 2 weeks • Other dose amount, as specified in the participant's parent protocol, administered over 1 hour (-10/+20 minutes, i.e., over 50 to 80 minutes) once every 2 weeks.
Use	Experimental
Sourcing	Provided centrally by the Sponsor
Packaging and Labeling	Study Intervention will be provided in vial. Each vial will be packaged and labeled per all applicable regulatory requirements and Good Manufacturing Practice Guidelines.

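### The escalation data cited for the overdose rule of twice the planned dose are not shown to reach 4800 mg, the trigger for planned 2400 mg

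*Protocol*

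**What the plan says.** Protocol section 8.4 defines overdose by one multiple of the planned dose, whatever that dose is: "any dose of bintrafusp alfa greater than 2 times of the planned dose within a 24-hour time period will be considered an overdose". The reason given is that in a dose escalation study "participants safely received up to 30 mg/kg bintrafusp alfa every 2 weeks", some of them at more than 2400 mg, "with no observed dose limiting toxicity at 30 mg/kg and not reaching maximum tolerated dose". For detail it points to the Investigator's Brochure (IB). It then limits the evidence itself: "Safety at significantly higher doses has not been clinically evaluated". It gives no largest dose in mg.

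Two overdose-specific actions follow. The infusion should be stopped and the participant watched closely. Reporting is wider than for ordinary dosing errors: "Even if not associated with an AE or a SAE, any overdose is recorded in the eCRF and reported to global patient safety", on an expedited basis. Both attach to an overdose as defined.

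Table 4 (section 6.1) allows planned 1200 mg every 2 weeks, "2400 mg: once every 2 weeks" and "2400 mg: once every 3 weeks". It also allows another dose taken from the parent protocol every 2 weeks. Sections 4.1 and 4.3 recommend a switch from mg/kg dosing to 1200 mg, but let participants on active treatment keep their mg/kg dose. Vials hold 600 mg.

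**The concern.** The trigger doubles with the planned dose, but the evidence cited for it stays the same. At 1200 mg, the cited escalation doses go past the trigger in absolute mg. At 2400 mg, the trigger lies well above anything section 8.4 describes, in a range that the section itself says was not studied.

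Section 8.4 asks for expedited reports even when no adverse event (AE) occurs, so it is meant to capture symptom-free dosing errors. For planned 2400 mg, such an error can reach a full double dose without meeting the definition. Section 2.2 calls experience at 2400 mg every 3 weeks limited, and the in-depth risk analysis in section 2.3.1 used 1200 mg every 2 weeks. What is at stake is the overdose-specific observation and the expedited report, in a study whose primary objective is safety. No estimate or test is involved.

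**Working it through.** **Inputs**
- Overdose multiple, more than 2 times the planned dose (section 8.4).
- Highest cited level, 30 mg/kg (section 8.4).
- Planned flat doses, 1200 mg and 2400 mg; vial content, 600 mg (Table 4).
- Body weights are assumptions, because the documents give none for the escalation study.

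**1. The protocol's own statement.** 30 mg/kg exceeds 2400 mg when weight is above 2400 / 30 = 80 kg. The statement that some doses were above 2400 mg is therefore consistent with the 30 mg/kg level.

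**2. Trigger against evidence, flat doses.** Trigger = 2 × planned dose. Weight at which 30 mg/kg equals the trigger = trigger / 30.

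| Planned dose | Trigger (more than) | Weight at which 30 mg/kg equals it |
|---|---|---|
| 1200 mg | 2 × 1200 = 2400 mg | 2400 / 30 = 80 kg |
| 2400 mg | 2 × 2400 = 4800 mg | 4800 / 30 = 160 kg |

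The first trigger lies below doses that section 8.4 says were given. The second would need an escalation participant of 160 kg, and the section reports none. At assumed weights of 70, 80 and 100 kg, 4800 mg is 68.6, 60 and 48 mg/kg. That is 2.3, 2.0 and 1.6 times the cited level.

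**3. Retained mg/kg doses.** 2 × 15 = 30 mg/kg, so any planned dose above 15 mg/kg has a trigger above the highest cited level. Planned 30 mg/kg gives 60 mg/kg.

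**4. The gap in vials, planned 2400 mg.** The planned dose is 2400 / 600 = 4 vials.

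| Vials given | Dose | Excess | Overdose under 8.4? | Weight at which 30 mg/kg equals the dose |
|---|---|---|---|---|
| 5 | 3000 mg | 25% | No | 100 kg |
| 6 | 3600 mg | 50% | No | 120 kg |
| 7 | 4200 mg | 75% | No | 140 kg |
| 8 | 4800 mg | 100% | No (exactly 2 times) | 160 kg |
| 9 | 5400 mg | 125% | Yes | 180 kg |

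**5. What a cap at the highest tested dose would do at 2400 mg.** Call that dose M; the trigger becomes the lower of 4800 mg and M. M is not in the documents, so a range is shown, taking M as 30 mg/kg in the heaviest escalation participant.

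| Assumed heaviest weight | M = 30 × weight | First whole-vial dose flagged |
|---|---|---|
| 81 kg | 2430 mg | 3000 mg (5 vials) |
| 100 kg | 3000 mg | 3600 mg (6 vials) |
| 120 kg | 3600 mg | 4200 mg (7 vials) |
| 150 kg | 4500 mg | 4800 mg (8 vials) |
| 160 kg | 4800 mg | 5400 mg (9 vials), as now |

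For planned 1200 mg nothing changes, because M is above 2400 mg by the protocol's own account.

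**The case against.** Several points on the other side stand.

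- **The maximum mg dose is not visible.** Section 8.4 says only that some doses were above 2400 mg and refers to the IB. A reader might infer that the data definitely stop short of 4800 mg. The 160 kg figure makes that plausible, but the documents show only that reaching 4800 mg is not demonstrated.
- **The trigger is a reporting definition.** A reader might infer that the protocol declares doses up to 4800 mg safe. It does not; it openly states the limit of its evidence.
- **Participants are not left unwatched.** Close observation after an overdose is worded as a recommendation in any case. Doses are given under medical supervision, with a second-person check and vial reconciliation (section 6.4). Intensive care or its equivalent must be immediately accessible, and delayed reactions are to be reported at once (section 8.3.6.1). Participants are asked about changes at each visit (section 8.3.2), and immediate safety concerns go to the Sponsor (section 8). Signs or sequelae of a suspected overdose count as AEs (Appendix 4), and an incorrect dose is an important protocol deviation (SAP section 10.2.1). None of these attaches overdose-specific observation or an expedited form to a symptom-free excess at or below the trigger. The Pharmacy Manual is not visible and may say more.
- **The contrast between doses depends on the unit.** Per kg, the 1200 mg trigger also exceeds 30 mg/kg below 80 kg. So does a correct 2400 mg dose: at 70 kg it is 2400 / 70 = 34.3 mg/kg. Exceeding 30 mg/kg therefore cannot by itself mark an overdose, and the argument for the flat doses has to be made in absolute mg.
- **A fixed 3000 mg cut-off does not follow from the evidence.** It is one extra vial, and equals 30 mg/kg only at 100 kg.

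The objection that a multiple of planned dose is a legitimate design choice is fair. However, section 8.4 rests the choice on specific data, and as described those data do not carry it at 2400 mg.

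**Conclusion.** The point holds as a modest gap between rule and rationale. The cited data support the 2400 mg trigger for planned 1200 mg in absolute mg. They are not shown to support the 4800 mg trigger for planned 2400 mg or, per kg, the trigger for retained doses above 15 mg/kg.

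For planned 2400 mg, the uncovered range runs from above 2400 mg up to and including 4800 mg, or one to four extra vials. Within it, a symptom-free excess escapes only the overdose-specific observation instruction and the expedited overdose report.

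This rests on 30 mg/kg being the highest level given, as section 8.4 says, and on no escalation participant being shown to weigh 160 kg or more. If the IB records a single dose of 4800 mg or more, the gap for planned 2400 mg closes and only the explanation in 8.4 is missing.

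Practical weight is small. The synopsis expects at least 10 participants, and the documents do not say how many receive 2400 mg or stay on mg/kg dosing. No endpoint, analysis or planned dose is affected. It is worth considering because it is cheap.

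**What to change.** In section 8.4, define overdose as any dose within 24 hours that exceeds the planned dose and is greater than the lower of:

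- (a) 2 times the planned dose, and
- (b) the highest single absolute dose in mg given in the escalation study, with the figure stated from the IB.

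This follows from the protocol's own rationale. The first condition ensures that a correctly given dose is never flagged, including a high mg/kg dose in a heavy participant. Planned 1200 mg is unaffected. For retained mg/kg doses the cap works in mg: it lowers the trigger whenever twice the planned dose exceeds the stated figure, and otherwise leaves it alone.

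A fixed 3000 mg trigger is not needed. The Sponsor may choose it for 2400 mg as a practical one-extra-vial rule, provided it is labelled as such and not as a toxicity limit.

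The cost is one sentence in section 8.4, a matching line in the pharmacy and overdose reporting instructions, and possibly a few extra overdose reports. The relative margin at 2400 mg becomes smaller than at 1200 mg: with a stated maximum of 3000 mg, for example, it is 25% against 100%. Dosing, endpoints and analyses stay the same.

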8.5 Pharmacokinetics

Not applicable

8.10 Health Economics OR Medical Resource Utilization and Health Economics

Not applicable

9.3 Populations for Analyses

The analysis populations are specified below (see [Table 7](#)). The final decision to exclude participants from any analysis population will be made during a data review meeting prior to database lock.

Table 7 **Analyses Sets**

Analysis Set	Description
Full (FAS)	For each parent study, the FAS will be defined as in the protocol of the parent study.
Safety (SAF)	For each parent study, the SAF will be defined as in the protocol of the parent study.

FAS = Full Analysis Set; SAF = Safety Analysis Set.

9.4 Statistical Analyses

Full details of all planned analyses will be described in the study IAP. Additional specifications may be provided in separate IAPs or addenda to existing Statistical Analysis Plans (SAPs) or IAPs of parent protocols. Major modifications of planned analyses will be reflected in a protocol amendment or in the clinical study report.

For the purpose of statistical analyses, data from the respective parent protocol will be merged with the data that were recorded under the rollover protocol for the participants of the parent study. Endpoint analyses will be based upon the analysis sets defined in the respective parent protocols.

For the rollover study, Follow-up analyses of safety and efficacy will be performed using the methodology described in the respective parent study protocol. The baseline time point from the parent study will be the baseline for safety and efficacy analyses.

In order to provide overall estimates of treatment effects, data will be pooled across study centers. The factor 'center' will not be considered in statistical models or for subgroup analyses due to the high number of participating centers in contrast to the anticipated small number of participants randomized at each center.

In general, continuous variables will be summarized using number (n), mean, standard deviation, median, first and third quartiles, minimum, and maximum. Categorical variables will be summarized using counts and percentages of participants in each category.

The calculation of proportions will be based on the number of participants in the analysis set of interest, unless otherwise specified in the study IAP. Statistical analyses will be performed using SAS® Software, Version 9.4 (SAS Institute Inc., Cary, NC, USA) or higher or ([R Core team, 2013](#)).

9.4.1 Efficacy Analyses

All efficacy analyses will be performed on the Full Analysis population.

As stated in the previous section, endpoint analyses will be based on the analysis sets defined in the respective parent protocols. Further details on efficacy endpoint analyses will be specified in the IAP and finalized before database lock.

9.4.2 Safety Analyses

All safety analyses will be performed on the Safety Analysis population defined in the protocol of the respective parent study.

The on-treatment period is defined as the time from the first dose of study intervention administration in the parent study to the last study intervention administration date + 30 days or the earliest date of subsequent anticancer drug therapy minus 1 day, whichever occurs first, unless otherwise stated.

Safety endpoints include, but are not limited to, TEAEs, SAEs, treatment-related AEs, AESIs, irAEs, and IRRs, as well as clinical laboratory assessments, vital signs, and ECOG PS as described in [Section 8.2](#).

The definitions, procedures for recording, evaluating, Follow-up, and reporting of AEs are described in [Appendix 4](#).

TEAEs are those events with onset dates occurring during the on-treatment period or if the worsening of an event is during the on-treatment period. Severity of AEs will be graded using the version of CTCAE toxicity grades used in the respective parent study.

All premature terminations will be summarized by primary reason for treatment discontinuation/withdrawal.

As stated in the previous section, safety analyses will focus on the occurrence of new AEs that have not been reported in the parent studies to assess if they lead to changes in the safety assessment, as given in the clinical study report of the respective parent study.

Participants will be analyzed according to the actual treatment they receive. The specifics for analysis methods will be defined in the IAP and finalized before database lock.

Endpoint	Statistical Analysis Methods
Primary To evaluate clinical safety of bintrafusp alfa in participants with solid tumors who continue treatment after completion of the primary/main analyses in parent bintrafusp alfa studies.	The safety endpoints will be tabulated using descriptive statistics using MedDRA preferred terms and system organ class.
Secondary	Not applicable

9.4.3 Other Analyses

Not applicable

Appendix 1 Abbreviations

AE(s)	Adverse event(s)
AESIs	Adverse events of special interest
AECI	Adverse events of clinical importance
anti-PD-L1	Antibody blocking programmed death-ligand 1
ALT	Alanine aminotransferase
ART	Antiretroviral therapy
AST	Aspartate aminotransferase
BOR	Best overall response
CI	Confidence Interval
CR	Complete response
CRF	Case report form
cSCC	Cutaneous squamous cell carcinoma
CT	Computed tomography
CCI	[REDACTED]
ECG	Electrocardiogram
ECOG PS	Eastern Cooperative Oncology Group Performance Status
eCRF	Electronic case report form
IWRS	Interactive Web Response System
FAS	Full Analysis Set
FSH	Follicle-stimulating hormone
GCP	Good Clinical Practice
HBV	Hepatitis B virus
HCV	Hepatitis C virus
HIV	Human immunodeficiency virus

HRT	Hormonal replacement therapy
IAP	Integrated Analysis Plan
IB	Investigator's Brochure
ICF	Informed Consent Form
ICH	International Council for Harmonisation
IEC	Independent Ethics Committee
IMP	Investigational Medicinal Product
irAEs	Immune-related adverse events
IRB	Institutional Review Board
IRR	Infusion-related reactions
IV	Intravenous
KA	Keratoacanthoma
MedDRA	Medical Dictionary for Regulatory Activities
MRI	Magnetic resonance imaging
NCI-CTCAE	National Cancer Institute-Common Terminology Criteria for Adverse Events
NCCN	National Comprehensive Cancer Network
NIMP	Non-Investigational Medicinal Product
NSCLC	Non-small cell lung carcinoma
OS	Overall survival
ORR	Overall response rate
PD	Progressive disease
PD-1	Programmed cell death protein 1
PD-L1	Programmed death ligand 1
CCI	[REDACTED]
PK	Pharmacokinetic(s)

PR	Partial response
PT	Preferred term
PS	Performance status
RECIST 1.1	Response Evaluation Criteria in Solid Tumors version 1.1
SAE(s)	Serious adverse event(s)
SD	Stable disease
SoA	Schedule of activities
SoC	Standard of care
SUSAR	Suspected unexpected serious adverse reaction
TGF β	Transforming growth factor β
TNBC	Triple-negative breast cancer
TEAE(s)	Treatment-emergent adverse event(s)
WOCBP	Woman of childbearing potential

Appendix 2 Study Governance

Financial Disclosure

Investigators and Sub-Investigators will provide the Sponsor with sufficient, accurate financial information, as requested, for the Sponsor to submit complete and accurate financial certification or disclosure statements to the appropriate regulatory authorities. This information is required during the study and for 1 year after completion of the study.

Informed Consent Process

- The Investigator or his/her representative will explain the nature of the study to the participant or his/her legally authorized representative (where allowed by local laws and regulations) and answer all questions on the study.
- Participants will be informed that their participation is voluntary.
- Participants or their legally-authorized representative (where allowed by local laws and regulations) will be required to sign a statement of informed consent that meets the requirements of 21 CFR 50; the Japanese ministerial ordinance on Good Clinical Practice (GCP); local regulations; internal conference on harmonization (ICH) guidelines; Health Insurance Portability and Accountability Act (HIPAA) requirements, where applicable; and the IRB/IEC or study center.
- The medical record will include a statement that written informed consent was obtained before the participant was enrolled in the study and the date the written consent was obtained. The authorized person obtaining the informed consent will also sign the ICF.
- If the ICF is updated during their participation in the study, participants will be re-consented to the most current, approved version.

Data Protection

- The Sponsor will assign a unique identifier to participants after obtaining their informed consent. Any participant records or datasets that are transferred to the Sponsor will contain the identifier only; participant names or any identifiable information will not be transferred.
- The Sponsor will inform participants that their personal study-related data will be used per local data protection and privacy laws. The level of disclosure will also be explained to the participant and pregnant partners (if applicable), who will be required to give consent for their data to be used, as specified in the informed consent.
- The participant will be informed that his/her medical records may be examined by Clinical Quality Assurance auditors or other Sponsor-appointed, authorized personnel, by appropriate IRB/IEC members, and by regulatory authority inspectors. All such persons will strictly maintain participants' confidentiality.

Study Administrative

The Coordinating or Principal Investigator listed on the title page represents all Investigators for decisions and discussions on this study, per ICH GCP. The Coordinating Investigator will

provide expert medical input and advice on the study design and execution and is responsible for the review and signoff of the clinical study report.

Details of structures and associated procedures will be defined in a separate Operations Manual.

Regulatory and Ethical Considerations

- This study will be conducted in accordance with the protocol and the following:
 - Consensus ethical principles derived from international guidelines, including the Declaration of Helsinki and Council for International Organizations of Medical Sciences (CIOMS) International Ethical Guidelines.
 - Applicable ICH GCP Guidelines
 - For studies with Japanese site, the Japanese ministerial ordinance on GCP
 - Applicable laws and regulations
- The protocol, protocol amendments (if applicable), ICF, Investigator Brochure, and other relevant documents (e.g., advertisements) will be submitted to an IRB/IEC for review and approval before the study is initiated.
- For studies with Japanese sites. The Sponsor initiates the study at a site after obtaining written approval from the Head of the study site, based on favorable opinion/approval from the concerned IRB.
- Any protocol amendments (i.e., changes to the protocol) will be documented in writing and require IRB/IEC approval before implementation of changes, except for changes necessary to eliminate an immediate hazard to study participants. When applicable, amendments will be submitted to the appropriate Health Authorities.
- The protocol and any applicable documentation will be submitted or notified to the Health Authorities in accordance with all local and national regulations for each site.

Emergency Medical Support

- The Sponsor or designee will provide Emergency Medical Support cards to participants for use during the study. These provide the means for participants to identify themselves as participating in a clinical study. Also, these give health care providers access to any information about this participation that may be needed to determine the course of medical treatment for the participant. The information on the Emergency Medical Support card may include the process for emergency unblinding (if applicable).
- The first point of contact for all emergencies will be the clinical study Investigator caring for the participant. Consequently, the Investigator agrees to provide his or her emergency contact information on the card. If the Investigator is available when an event occurs, they will answer any questions. Any subsequent action (e.g., unblinding) will follow the standard process established for Investigators.

When the Investigator is not available, the Sponsor provides the appropriate means to contact a Sponsor (or designee) physician. This includes provision of a 24-hour contact number at a

call center, whereby the health care providers will be given access to the appropriate Sponsor (or designee) physician to assist with the medical emergency.

Clinical Study Insurance and Compensation to Participants

Insurance coverage will be provided for each country participating in the study. Insurance conditions will meet good local standards, as applicable.

The Sponsor is entirely responsible for AEs that are associated with this study and cause damage to the health of the participants, except for AEs caused by an intentional and/or significant deviation on the part of the Investigator, the study site, and/or the participant. The Sponsor takes out insurance to fulfill the responsibility.

Clinical Study Report

After study completion, the Sponsor will write a clinical study report in consultation with the Coordinating Investigator or other relevant study-appointed committees or groups.

Publication

- The results of this study may be published or presented at scientific meetings. If this is foreseen, the Investigator agrees to submit all manuscripts or abstracts to the Sponsor before submission. This allows Merck to protect proprietary information and to provide comments.
- The Sponsor will comply with the requirements for publication of study results. Per standard editorial and ethical practice, the Sponsor will generally support publication of multicenter studies only in their entirety and not as individual site data.
- Authorship will be determined by agreement and in line with International Committee of Medical Journal Editors authorship requirements.

Dissemination of Clinical Study Data

After completion of the study, a Clinical Study Report according to ICH Topic E3 will be written by the Sponsor or the designated CRO in consultation with the Coordinating Investigator. The first publication will be a publication of the results of the analysis of the endpoints that will include data from all study sites that participated in the parent study. The Investigators will inform the Sponsor in advance of any plans to publish or present data from the study. Any publications and presentations of the results (abstracts in journals or newspapers, oral presentations etc), either in whole or in part, by Investigators or their representatives will require pre-submission review by the Sponsor.

The Sponsor will not suppress or veto publications, but maintains the right to delay publication in order to protect intellectual property rights.

Data Quality Assurance

- All participant study data will be recorded on printed or eCRFs or transmitted to the Sponsor or designee electronically (e.g., laboratory data). The Investigator is responsible for verifying that data entries are complete, accurate, legible, and timely by physically or electronically signing the CRF. Details for managing CRFs are in the Study Reference Manual.

- The Investigator will maintain accurate documentation (source data) that supports the information in the CRF.
- The Investigator will permit study-related monitoring, quality assurance audits, IRB/IEC review, and regulatory agency inspections and provide direct access to the study file and source data.
- Quality Tolerance Limits (QTLs) will be pre-defined in the applicable project management database to identify systematic issues that can impact participant safety and/or reliability of study results. These pre-defined parameters will be monitored during the study and important deviations from the QTLs and remedial actions taken will be summarized in the clinical study report.
- Monitoring details describing strategy (e.g., risk-based initiatives in operations and quality such as Risk Management and Mitigation Strategies and Analytical Risk-Based Monitoring), methods, responsibilities and requirements, including handling of noncompliance issues and monitoring techniques (central, remote, or on-site monitoring) are in the Monitoring Plan or contracts.
- The Sponsor or designee is responsible for data management of this study, including quality checking of the data and maintaining a validated database. Database lock will occur once quality control and quality assurance procedures have been completed. Details will be outlined in Data Management documents and procedures.
- Study Monitors will perform ongoing source data verification to confirm that data in the CRF are accurate, complete, and verifiable; that the safety and rights of participants are being protected; and that the study is being conducted per the currently approved protocol and any other study agreements, ICH GCP, the Japanese ministerial ordinance on GCP, and all applicable regulatory requirements.
- The Investigator will retain records and documents, including signed ICFs, pertaining to the conduct of this study for 15 years after study completion, unless local regulations, institutional policies, or the Sponsor requires a longer retention. No records may be destroyed during the retention period without the Sponsor's written approval. No records may be transferred to another location or party without the Sponsor's written notification.

Source Documents

- Source documents provide evidence for the existence of the participant and substantiate the integrity of the data collected.
- The Investigator will maintain source documents that support the data recorded in the CRFs.
- Data recorded on CRFs that are transcribed from source documents will be consistent with the source documents or the discrepancies will be explained. The Investigator may need to request previous medical records or transfer records, depending on the study. Also, current medical records will be available.
- Source documents are stored at the site for the longest possible time permitted by the applicable regulations, and/or as per ICH GCP guidelines, whichever is longer. The Investigator or a record retainer designated by the Head of the study site ensures that no destruction of medical records is performed without the Sponsor's written approval.

-
- Definition of what constitutes source data is found in case report form guidelines.

Study and Site Start and Closure

- The study start date is the date when the clinical study will be open for recruitment.

Study and Site Termination

- The Investigator may initiate site closure at any time, provided there is reasonable cause and enough notice is given in advance of the intended closure.
- Reasons for the early closure of a study site by the Sponsor or Investigator may include:
 - Failure of the Investigator to comply with the protocol, the requirements of the IRB/IEC or local health authorities, the Sponsor's procedures, or GCP guidelines
 - Inadequate recruitment of participants by the Investigator
 - Discontinuation of further development of the Sponsor's compound
- If the study is prematurely terminated or suspended, the Sponsor will promptly inform the Investigators, the IECs/IRBs, the regulatory authorities, and any third-party service providers used in the study of the reason for termination or suspension, as specified by the applicable regulatory requirements. The Investigator will promptly inform the participants and assure appropriate participant therapy and/or Follow-up.

